- 2) Subjects with known cystic kidney disease or posterior ureteral valves (subjects with solitary kidney, single multicystic/dysplastic kidney, hydronephrosis will not be excluded if renal function is preserved)
- 3) Subjects with known metabolic disorder
- 4) Premature infants born < 30 weeks gestation and < 30 days old due to risk of intraventricular hemorrhage

Subjects in severe cardiogenic shock post-operative requiring extra-corporeal membrane oxygenation (ECMO) or left ventricular assist device (LVAD) will be withdrawn from the study.

IV. Randomization and Blinding

Subjects will be randomized to the treatment group or control group in a 1:1 ratio to receive sodium bicarbonate (treatment group) or placebo (control group). Allocation will be based on random, computer-generated numbers in permuted blocks of 10. Study drug and placebo will be prepared and dispensed by the pharmacy according to randomization. The treatment will be administered in an identical fashion to subjects in both arms. The investigators involved in the study, clinicians and study subjects will be blinded to the treatment assignment.

V. Study Procedures

The outline of study procedures is as follows:

| Study Procedures | | | | | | | | | | | |
|-------------------------------------|-----------|---------------|--|-----------------|------|------|-------|-------|-------|---------|---|
| | Screening | Pre-Operative | | Intra-Operative | 2 hr | 4 hr | 12 hr | 24 hr | 48 hr | 30 days | |
| Review Inclusion/Exclusion Criteria | x | | I N T E R V E N T I O N | | | | | | | | |
| Informed Consent/Assent | x | | | | | | | | | | |
| Randomization | | x | | | | | | | | | |
| Demographics/Medical History | x | | | | | | | | | | |
| Height and Weight | x | x | | | | | | | | | x |
| Serum creatinine/BUN | x | x | | | | x | x | x | x | x | x |
| Serum electrolytes | x | x | | | x* | x | x | x | x | x | x |
| Urine pH | | x | | | x* | x | x | x | x | x | |
| CBC with differential | x | x | | | | | | | | | |
| Serum NGAL | | x | | | | x | x | x | x | x | |
| Serum pH | | x | | | x* | x | x | x | x | x | |
| Urine Output Monitoring | | x | | | x | x | x | x | x | x | |

* Serum and urine pH and serum electrolytes will be done at the discretion of anesthesia and bypass team as per protocol.

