Treatment Arm: Patients randomized to the intervention of receiving NaHCO₃ perioperatively will initially receive the current standard anesthetic and perfusion approach at CCMC, which includes a cardiopulmonary pump priming solution containing 0.2mEq per milliliter of crystalloid. At the start of the surgery, the patient will begin to receive NaHCO₃ as a continuous infusion of D5% 1/3NS + 100 meq/L NaHCO₃ + 20 meq/L KCl at maintenance IVF (solution contains ~154 meq of sodium which is equivalent to normal saline). The strength of NaHCO₃ is based on a dose of 150 meq/m²/day (reference range 120-200mEq/m²/day [Lexicomp, 18th Ed., 2011-12]) and IVF maintenance of 1500 ml/m²/day. While the patient is undergoing CPB, calculated base deficits more negative than -3 will be corrected by giving NaHCO₃ according to the formula: base deficit * patient weight in kilograms/ 3. Tromethamine (THAM) may be used in the neonatal population while undergoing CPB if the serum sodium levels have increased to greater than 145 mEq/dL. Blood gas serum sodium, potassium and calcium will be monitored during the surgery and corrections will be made by the anesthesiologist. The NaHCO₃ infusion will continue for the first 24 hours after the discontinuation of CPB (based on current data from CCMC PICU: 85% of patients who develop AKI do so in the first 24 hours, and duration of AKI is <48 hours in 75% patients (reference Aydin, Annals of Thoracic Surgery, 2012). After 24 hours of receiving the NaHCO₃ infusion, the IVF administered to the patient will be the standard solutions used in the PICU at CCMC, notably a sodium concentration with dextrose along the spectrum of D5 0.33% NaCl through D5 0.45% NaCl, depending on the patient's serum electrolyte profile.

Control Arm: At the start of surgery, patients in the control arm will receive D5% Normal Saline + 20 meq/L KCL at maintenance IVF. The standard approach to perfusion for CPB, including the pump prime solution containing NaHCO₃ as well as replacement of NaHCO₃ for calculated base deficits will be administered as described above. After 24 hours, standard IVF, not containing NaHCO₃ or Na acetate will be administered for

the duration of the PICU stay as required, determined by the clinicians primarily caring for the patient postoperatively.

d. Hospital Course

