To ensure that the chosen dose of sodium bicarbonate adequately alkalinizes the urine, we will briefly halt enrollment to blindly review urine pHs of the first 10 randomized subjects. The research nurse will be blinded to the patients' enrollment arm and the information regarding the results of the urine pH will not be available to the investigators until this interim analysis to assure appropriate blinding during the treatment of each patient. Since we have blocked randomization in groups of 10, we expect that half of the subjects will receive treatment with Sodium Bicarbonate. Therefore, we expect half of the subjects to have urine pH close to 7. If we find that urine is not adequately alkalinized, we will halt the study and submit a modification to the IRB to alter the dose of sodium bicarbonate.

VI. Study Outcomes

Demographic and Clinical Data

The medical record will be abstracted for the following variables: age, gender, diagnosis, previous surgical history, race, left ventricular ejection fraction on baseline echo, and current medications. Surgical parameters of cardio-pulmonary bypass time, ischemic time, surgical procedure, surgical complexity score, lowest temperature, use of circulatory arrest, use of cerebral perfusion, renal NIRS (measure of oxygen saturation of the renal vessels), medications administered, pH range, urine pH, surgical time, post-bypass time, estimated blood loss, and blood products administered will be measured. Cumulative fluid balance (daily Ins and Outs), hospital and intensive care unit length of stay, need for and duration of dialysis and medical complications will be recorded.

Serum NGAL is a biomarker of early AKI that often increases before serum creatinine. Specifically for this research study, serum NGAL and creatinine level will be drawn at the time of surgery and at 2, 4, 12, 24, and 48 hours.

As per routine care, creatinine will then be measured daily. pRIFLE level will be calculated on the maximum creatinine attained.

| pRIFLE Criteria | | |
|------------------------|---|---|
| | GFR | Urine Output |
| Risk | decrease by 25% | 0.5 mL/kg/h for 8 hours |
| Injury | decrease by 50% | 0.5 mL/kg/h for 16hours |
| Failure | decrease by 75% or GFR <35 | 0.3 mL/kg/h for 24 hours or anuric for 12 hours |
| Loss | Persistent failure 4 weeks | |
| End stage | End-stage renal disease (persistent failure 3 mo) | |

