Creatinine clearance will be estimated by the Schwartz formula ($k \times ht \text{ (cm)} / \text{creatinine}$; $k = 0.4$ premature, $k = 0.55$ females and pre-pubertal males <13 , $k = 0.7$ pubertal males). NGAL will be measured by enzyme-linked immunosorbent assay. Urine pH will be measured at 2, 4, 12, 24 hours post surgery, and as described above, the investigators will be blinded to these results. Serum pH and electrolytes will be measured at 2, 4, 12, 24 hours. NGAL and urine pH will be measured specifically for the purpose of performing this research study. Serum pH is routinely measured as standard practice in post-operative cardiothoracic surgery patients during surgery, and at hours 2, 12, and 24 hours post-operatively.

PART E. Statistical Issues

I. Statistical Analysis

Statistical analyses will be done using SPSS 18.0 (SPSS Inc., Chicago, IL) statistical package. A two-tailed p-value < 0.05 is the criterion for statistical significance. Intention to treat analysis will be done. Descriptive statistics will be used to characterize outcome measures in subjects. Means, standard deviations, 95% confidence intervals, medians, and minimum and maximum values will be tabulated and reported for all continuous variables. Frequency counts and percentages will be used for categorical variables. The distributions of each outcome will be examined for normality. Baseline demographic and clinical data of the two arms will be examined. Differences in means in the treatment group will be compared to the control group using Student’s t-test, or the Wilcoxon Rank Sum test if the data are not normally distributed. Differences in proportions will be assessed using the chi-square test.

Specific Aims:

1. To analyze the primary outcome, chi-square will be conducted to compare the proportion of subjects who develop AKI by pRIFLE criteria in the two groups.

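### The first-10 dose check pools both arms, so it identifies an adequate dose only if few controls have alkaline urine; a by-arm reading is a cheap improvement

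*Combined protocol and SAP*

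**What the plan says.** V.g describes the dose check: "we will briefly halt enrollment to blindly review urine pHs of the first 10 randomized subjects". Randomization is in permuted blocks of 10, so five of these children are treated and five are controls. The only benchmark is "we expect half of the subjects to have urine pH close to 7". The consequence of failure is stated as "If we find that urine is not adequately alkalinized, we will halt the study" and submit a changed dose to the IRB. V.g gives no pH cut-off, no pass count and no sampling time.

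V.c (Control Arm) gives controls bicarbonate during bypass as well: "The standard approach to perfusion for CPB, including the pump prime solution containing" bicarbonate, and replacement "for calculated base deficits will be administered as described above". The rule referred to, in the Treatment Arm paragraph, corrects base deficits beyond -3 by base deficit × weight / 3. V.b allows further boluses in either arm and calls them infrequent.

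On timing, V.c says the study "infusion will continue for the first 24 hours after the discontinuation of CPB". Section VI says "Urine pH will be measured at 2, 4, 12, 24 hours post surgery", and V.d adds a 48 h sample. On allocation, Section IV says "Study drug and placebo will be prepared and dispensed by the pharmacy according to randomization".

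**The concern.** The step from half alkaline to adequate dose treats every alkaline urine as coming from a treated child. Without arm labels, an alkaline control cannot be told from a treated child who responded. Controls do receive bicarbonate on bypass, so the possibility is real, and V.g does not address it.

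This is the plan's only stated check that 150 mEq/m²/day alkalinizes the urine before enrolment continues. If a weak dose passes, the remaining 132 − 10 = 122 children are enrolled on it, and the early opportunity to raise the dose is gone.

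**Working it through.** **Inputs from the documents.** Ten children, five per arm (Section IV, V.g); expected result, half near pH 7 (V.g). **Assumptions.** pT and pC, the shares of treated children and controls with urine near pH 7, and every pass count. The documents give none of these.

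**The plan's own figure.** Expected count = 5·pT + 5·pC. With pT = 1 and pC = 0 this is 5 of 10, the stated half. But (0.8, 0.2) gives 4 + 1 = 5, and (0.5, 0.5) gives 2.5 + 2.5 = 5. The last is an infusion that adds nothing, so the pooled count alone cannot separate it from the first.

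**Pass probability, pooled.** The count is Bin(5, pT) + Bin(5, pC). For a weak dose, pT = 0.4:

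| pC | pass at ≥4 of 10 | pass at ≥5 of 10 |
|---|---|---|
| 0 | 9% | 1% |
| 0.2 | 35% | 14% |
| 0.4 | 62% | 37% |

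The first row shows that the pooled check works when controls stay acidic. The stricter count has its own cost: at pT = 0.9 and pC = 0 a good dose passes 92% of the time at ≥4 but only 59% at ≥5.

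**By arm, treated children only.** P(Bin(5, pT) ≥ 4) is 9% at pT = 0.4 whatever pC is, and 92% at 0.9. When the arms do not differ it still passes 19% at 0.5/0.5 and 34% at 0.6/0.6, so the rule needs the controls in it.

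**By arm, with controls.** Pass if at least 4 of 5 treated are at pH 7 or above and treated minus control is at least 2. Then P = P(T=4)·P(C≤2) + P(T=5)·P(C≤3).

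- 0.4/0.4: 0.0768 × 0.683 + 0.0102 × 0.913 = 0.062, or 6%.
- 0.5/0.5: 0.156 × 0.500 + 0.031 × 0.8125 = 0.103, or 10%.
- 0.9/0: 0.328 + 0.590 = 0.919, or 92%.
- 0.9/0.4: 0.328 × 0.683 + 0.590 × 0.913 = 0.763, or 76%.

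**How much bicarbonate controls may get.** A correction at the -3 trigger is 3 × weight / 3 = 1 mEq/kg. Assume body surfaces of 0.22, 0.47 and 0.8 m² at 3.5, 10 and 20 kg. The infusion then delivers 150 × area / 24 = 1.4, 2.9 and 5.0 mEq/h, so one minimum correction equals about 2.5, 3.4 and 4.0 hours of infusion. This compares amounts given. It does not show that the correction alkalinizes the urine.

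**The case against.** The strongest objection is that everything turns on pC, which is unknown. Base-deficit correction treats existing acidosis and may only neutralize it, and V.b calls other boluses infrequent. No passage supports a control share of 0.4. The dose also has a rationale: Part C places 150 mEq/m²/day inside a 120–200 range used for urinary alkalization, although that reference uses twice the fluid volume. All of this stands, and it keeps the point conditional.

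Second, the reviewer will see serial values for each child, including a pre-operative one, not one yes/no result. Later samples should separate the arms better, because bypass dosing ends with bypass. A blinded 12 h reading with a fixed cut-off would remove much of the difficulty. That is fair, but V.g does not confine the review to late samples, and even at 12 h a pooled reading cannot attribute an alkaline urine to an arm.

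Third, the blind review is deliberate. It is, but the pharmacy already works from the allocation, and Part H provides an independent reviewer. Under V.g the investigators receive the pH results at the interim review. If the dose works, those values hint at allocation, so releasing only the decision protects the blind at least as well.

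A reader might infer that bypass bicarbonate in controls biases the primary comparison, or that a null AKI result could not be interpreted if the check passed wrongly. The documents support neither. The rule for bypass bicarbonate is the same in both arms. Urine pH is collected in all children, so separation can be tabulated by arm at unblinding.

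**Conclusion.** The point holds conditionally. The pooled benchmark identifies an adequate dose only if few controls are alkaline, and the plan neither shows this nor allows for it. If pC is near zero, the check performs as intended. At pC of 0.2 to 0.4, a dose that alkalinizes 40% of treated children passes 35% to 62% of the time at ≥4 of 10, or 14% to 37% at ≥5 of 10. These figures rest on assumed shares and pass counts; the true size of the risk is unknown.

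A reader might go further and conclude that the dose is inadequate or that controls are in fact alkalinized. The documents contain no control urine pH data and give no ground for either. What is at risk is the early chance to correct the dose. The validity of the primary analysis is not affected. The change is worth making because it is cheap and reads correctly whichever way pC turns out.

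**What to change.** Amend V.g as follows.

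1. The pharmacy or the Part H independent reviewer reads the urine pH of the first 10 children by arm.
2. Decide on the 12 h sample, when the infusion is running and bypass dosing is over. The 24 h sample is less safe: it is timed from surgery, while the infusion stops 24 hours after bypass ends, so it could fall after the infusion has stopped.
3. Set the rule in advance and include the controls, for example at least 4 of 5 treated at pH 7 or above and at least 2 more treated than control.
4. Give investigators only the decision.
5. If controls are also alkaline, report the lack of separation to the independent reviewer and the IRB. Bypass care stays as it is.

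**Cost.** A short amendment and one unblinded look outside the investigator team; no new samples. The downside is that a good dose is flagged more often when many controls are alkaline (it passes 76% of the time at 0.9/0.4, against 92% at 0.9/0). In that case the flag reports poor separation between the arms, and step 5 applies.

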Treatment Arm: At the start of the surgery, the patient will receive NaHCO₃ as a continuous infusion of D5% 1/3NS + 100 meq/L NaHCO₃ + 20 meq/L KCl at maintenance IVF (solution contains ~154 meq of sodium which is equivalent to normal saline). The NaHCO₃ infusion will continue for the first 24 hours after the discontinuation of CPB. After 24 hours of receiving the NaHCO₃ infusion, the IVF administered to the patient will be the standard solutions used in the PICU at CCMC.

Control Arm: At the start of surgery, patients in the control arm will receive D5% Normal Saline + 20 meq/L KCl at maintenance IVF. After 24 hours, standard IVF, not containing NaHCO₃ or Na acetate will be administered for the duration of the PICU stay as required, determined by the clinicians primarily caring for the patient postoperatively.

Primary Outcome Measure: The efficacy of sodium bicarbonate on prevention of AKI will be tested by comparing the proportion of subjects in each of the treatment arms who progress to AKI as measured by the Pediatric Risk, Failure, Loss of Function, and End-Stage Renal Disease (pRIFLE) criteria or an absolute increase in creatinine of 0.3mg/dl.

Secondary Outcome Measures:

1. Duration of acute kidney injury
2. Cumulative fluid balance
3. Hospital and intensive care unit length of stay
4. Need for dialysis
5. Progression to pRIFLE criteria F
6. Association of NGAL as a biomarker to predict development of acute kidney injury
7. Length of mechanical ventilation
8. Change in acid-base status

II. Study Sites

Subjects will be recruited from the Cardiothoracic Surgery Division of the Cohen Children's Medical Center of New York of North Shore-LIJ Health Systems (CCMC) in New Hyde Park, New York

III. Study Subjects

Patients from CCMC come from a large geographic area with a diverse racial composition. There are currently 150 children ≤ 18 years that undergo cardiac surgery with cardiopulmonary bypass per year at CCMC. Consecutive patients scheduled for cardiac surgery who meet eligibility criteria will be invited to participate in the study.

Eligibility criteria include:

Inclusion Criteria

- 1) Subjects age ≤ 18 years
- 2) Subjects scheduled for cardiac surgery with cardiopulmonary bypass

Exclusion Criteria

- 1) Subjects with abnormal creatinine clearance (< 90 ml/min/1.7m²) as measured by the Schwartz formula

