2. Student’s t-test or Wilcoxon Rank Sum test for non-normally distributed variables will be used to compare values of duration of acute kidney injury, fluid balance, hospital length of stay, need for dialysis, and progression to kidney failure between groups. Pearson correlation and linear regression will be used to examine the association between duration of acute kidney injury, fluid balance, hospital length of stay, need for dialysis, and progression to kidney failure and development of AKI. Regression analysis will be adjusted for sex, age and race. Variables may be log transformed to improve the fit of the models.
3. Pearson correlation and linear regression will be used to analyze the association of NGAL with development of AKI.

II. Sample Size Estimates

Sample size estimates were calculated for the primary outcome of proportion that develop AKI in each of the two groups. Sample sizes were considered based on various effect sizes. Assuming 50% risk of AKI from our previous work, a drop from 50% AKI to:

35% would need 170 per group

30% would need 93 per group

25% would need 66 per group

20% would need 44 per group

In the literature, studies have used reductions between 20-35%. We aimed for somewhere in between. The comparison of 66 subjects in the treatment group and 66 subjects in the control group provides 80% power ($\alpha = 0.05$) to detect a difference from 0.5 in the control group to 0.25 (that is a 50% reduction in AKI) in the treatment group. nQuery software was utilized to calculate sample size.

III. Limitations

The proposed study is limited by the small sample size and heterogenous population. Given these limitations, we believe the results of the proposed study will be able to be generalized to the pediatric cardiac surgery population.

PART F. PROTECTION OF HUMAN SUBJECTS

Risk to Subjects

a. Human Subjects Involvement and Characteristics

The proposed study will involve human subjects, in particular, children and adolescents aged ≤ 18 years of age. The purpose of the study is to examine cardiac surgery in a pediatric population, therefore, other age groups are excluded from this study. Other inclusion/exclusion criteria are listed elsewhere in the protocol. This vulnerable population will be protected. Assent will be obtained from the participants and participants may withdraw from the study at any time.

b. Potential Risks

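### Aim 2 puts two yes/no renal outcomes under the t-test or Wilcoxon test, names no exact test for sparse counts, and correlates AKI with two outcomes that depend on AKI by definition

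*Combined protocol and SAP*

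**What the plan says.** All the rules are in the Combined protocol and SAP, PART E, section I (Statistical Analysis).

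- **General rules.** "Differences in proportions will be assessed using the chi-square test". For description, "Frequency counts and percentages will be used for categorical variables", while confidence intervals are mentioned only for continuous variables: "Means, standard deviations, 95% confidence intervals, medians, and minimum and maximum values will be tabulated and reported for all continuous variables".
- **Specific Aims, item 2, comparison of arms.** The "t-test or Wilcoxon Rank Sum test for non-normally distributed variables will be used to compare values of duration of acute kidney injury" and four further outcomes; the list ends "need for dialysis, and progression to kidney failure between groups".
- **Specific Aims, item 2, association.** Pearson correlation and linear regression, adjusted for sex, age and race, are to relate the same five outcomes to AKI. That list ends "need for dialysis, and progression to kidney failure and development of AKI".

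The outcome definitions show the data type. PART D, section I lists need for dialysis and "Progression to pRIFLE criteria F" as secondary outcomes 4 and 5. PART D, section VI says that "need for and duration of dialysis and medical complications will be recorded", so a duration of dialysis will exist, but the listed outcome is need.

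**The concern.** Need for dialysis and reaching pRIFLE F either happen to a child or do not. A t-test or rank test treats them as measured values, and the section's own rule for proportions points elsewhere. An analyst following the plan could defend either route.

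The larger question is what happens with few events. These are the most serious renal outcomes in the trial. If only a handful of children reach them, a small imbalance could be declared significant by a large-sample test when an exact test would not support it. If no child is dialysed, the t-test cannot be calculated.

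The association sentence has a different defect. It asks whether AKI is associated with two quantities that can be non-zero only in a child with AKI. A significant result there would tell the reader nothing.

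**Working it through.** **Inputs.** 66 children per arm, 132 in total (PART D, section I; PART E, section II); two-sided 0.05 (PART E, section I). The planned size is used here only as the group size; it reproduces with the continuity-corrected two-proportion formula for 50% v 25% at 80% power (66; 58 without the correction). The documents give no expected dialysis or failure rate and no figure for these comparisons, so the counts and rates below are assumptions.

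**Step 1: 4 v 0 events, worked in full.**

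- t-test: difference 4/66 = 0.0606. Pooled variance = 4 × (1 − 4/66) / 130 = 0.0289. Standard error = √(0.0289 × 2/66) = 0.0296. t = 2.05 on 130 df, p=0.043.
- Uncorrected chi-square: 132 × (4 × 66)² / (66 × 66 × 4 × 128) = 4.125, p=0.042.
- Fisher: 2 × C(66,4) / C(132,4) = 2 × 720,720 / 12,082,785 = 0.119.

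**Step 2: other sparse tables.**

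| Events | t-test | Wilcoxon | Chi-square, uncorrected | Fisher |
|---|---|---|---|---|
| 4 v 0 | 0.043 | 0.043 | 0.042 | 0.119 |
| 5 v 0 | 0.023 | 0.023 | 0.023 | 0.058 |
| 6 v 0 | 0.012 | 0.013 | 0.012 | 0.028 |
| 7 v 1 | 0.029 | 0.029 | 0.029 | 0.062 |
| 8 v 2 | 0.049 | 0.049 | 0.048 | 0.096 |

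Over 634 tables with unequal counts, the t-test and uncorrected chi-square never disagreed at 0.05. A Yates-corrected chi-square would behave much like Fisher (4 v 0: 0.128; 5 v 0: 0.068), but the plan does not say which form it means.

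**Step 3: overall type I error.** Summing binomial probabilities over all tables, with the same true rate in both arms:

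| True rate | t, Wilcoxon, chi-square | Fisher |
|---|---|---|
| 1% | 0.5% | 0.01% |
| 2% | 2.3% | 0.1% |
| 5% | 4.7% | 1.2% |
| 8% | 5.2% | 2.0% |
| 10% | 5.1% | 2.4% |

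**Step 4: type I error given the total number of events.** With the total fixed, the split between arms is hypergeometric. The t-test's false-positive rate is 0% for totals of 1 to 3, 11.9% for 4, 5.8% for 5, 2.8% for 6, 1.3% for 7, 6.2% for 8, 3.3% for 9 and 9.6% for 10. Over totals of 1 to 20 it ranges from 0% to 11.9% and is below 5% for 12 of the 20.

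**Step 5: intervals, if a t-based one were reported.** At true rates of 3% v 1% the pooled-t 95% interval covers 85.8% of the time, and the Newcombe interval 99.4%. At equal rates of 2% and 5% the t interval covers 97.7% and 95.3%. With 0 v 0 events it is 0 to 0, while Newcombe gives −5.5 to +5.5 percentage points. The chance of no events among 132 children is 0.99^132 = 27% at a 1% rate and 0.98^132 = 7% at 2%.

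**Step 6: the built-in association.** The planning rates imply about 33 + 16.5 ≈ 50 AKI cases among 132. If k failures all lie inside those 50, as they must, r = √[k × 82 / (50 × (132 − k))]. For k = 3, r = √(246/6,450) = 0.195, p=0.025. For k = 2, p=0.069; for k = 1, p=0.20. Failure is a grade of AKI in the pRIFLE table (PART D, section VI), and adding the 0.3 mg/dl creatinine criterion of PART D, section I does not change that.

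**The case against.** The strongest reply is that the inconsistency has almost no numerical effect. A reader might infer that the p-values are wrong because the t-test replaces the plan's own rule for proportions. The documents do not support that: following the rule with an uncorrected chi-square gives the same answers (steps 1 and 2).

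A reader might also infer, from the 11.9% and 9.6% in step 4, that the t-test rejects too often in general. It does not. Those are the two highest values among totals of 1 to 20, and averaged over totals the error rate is about 5% or less. Preferring Fisher is partly a preference for a conditional and conservative test.

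A third inference, that the trial will report faulty intervals, goes beyond the text. The plan specifies no between-arm interval for these outcomes, so step 5 is conditional on someone producing one.

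All of that stands, as does the point that the correlation does not compare arms and so cannot bias the treatment effect. What remains is that two rules cover the same outcomes, no exact test is named for the sparse case, and two of the planned correlations are circular. The last does not depend on the example in step 6: whatever the p-value, the association is fixed in advance by the definitions.

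**Conclusion.** The point holds in limited form. Aim 2 states the wrong kind of test for two binary secondary outcomes and contradicts the rule for proportions in the same section. Replacing it with uncorrected chi-square alone would settle the wording but leave the p-values as they are. The substantive gap is the lack of an exact test: with 66 per arm, 4 v 0, 5 v 0, 7 v 1 and 8 v 2 are all nominally significant under the named tests and not under Fisher's.

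This matters only if events are few, which is an assumption because the documents give no rates. General inflation of type I error is not shown. The circular correlation of AKI with its own duration and its own severest acute grade needs no assumption about rates. The primary chi-square comparison of AKI is unaffected.

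**What to change.** In PART E, section I, Specific Aims, item 2:

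1. Remove need for dialysis and progression to failure from the t-test/Wilcoxon sentence. State that each is reported as a count and percentage per arm, compared by Fisher's exact test, with the risk difference and a Newcombe or exact 95% interval.
2. If Fisher is to apply only when an expected count is below 5, write that trigger in now. Under it, 8 v 2 (expected count 5 per arm) would still go to chi-square, so using Fisher throughout for these two outcomes is simpler.
3. In the correlation/regression sentence, delete AKI duration and progression to failure as correlates of development of AKI. For need for dialysis, use an exact test or a Firth logistic model in place of Pearson correlation and linear regression.

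The cost is two sentences of wording and no new data. The price of Fisher is conservatism: its actual size is about 1.2% at a 5% event rate and 2.4% at 10%, so fewer small imbalances would be called significant. Reporting the risk difference with its interval keeps such imbalances visible.
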